#### 5 STUDY POPULATION

# 5.1 Number of Subjects (approximate)

Approximately 600 subjects will be screened to enroll approximately 350 subjects across approximately 17 sites.

[figure not shown]
# 5.2 Study Population Characteristics

All subjects must be at least 18 years of age, be of either sex and of any race, have a subject-reported history of dry eye disease, and meet all of the inclusion criteria and none of the exclusion criteria.

#### 5.3 Inclusion Criteria

# Each subject must meet each of the following criteria:

- 1. 18 years of age (either gender and any race);
- 2. Ability to provide written informed consent and sign the Health Information Portability and Accountability Act (HIPAA) form;
- 3. Reported history of dry eye for at least 6 months prior to Visit 1;
- 4. Reported history of use or desire to use eye drops for dry eye symptoms within 6 months of Visit 1;

Confidential Page 19 of 60

#### 5.4 Exclusion Criteria

#### Each subject may not meet any of the following criteria:

- 1. Clinically significant slit lamp findings at Visit 1 that may include active blepharitis, meibomian gland dysfunction (MGD), lid margin inflammation, or active ocular allergies that require therapeutic treatment, and/or in the opinion of the investigator may interfere with study parameters;
- 2. Diagnosis of an ongoing ocular infection (bacterial, viral, or fungal), or active ocular inflammation at Visit 1;
- 3. Contact lens use within 7 days of Visit 1 or anticipate using contact lenses during the trial;
- 4. Artificial tear eye drop use within 2 hours of Visit 1 or within 24 hours of Visit 2 (drops cannot be used on the day of Visit 2 or Visit 3;
- 5. Previous laser-assisted *in situ* keratomileusis (LASIK) surgery within the last 12 months;
- 6. Cyclosporine 0.05% or 0.09% or lifitegrast 5.0% ophthalmic solution use within 90 days of Visit 1;
- 7. Systemic corticosteroid therapy or other immunomodulator (not including inhaled corticosteroids) within 14 days of Visit 1 or anticipate such therapy throughout the study period;
- 8. Planned ocular and/or lid surgeries over the study period or any ocular surgery within 6 months of Visit 1;
- 9. Temporary punctal plugs during the study that have not been stable within 30 days of Visit 1;
- 10. Use of and unwillingness to discontinue topical ophthalmic prescriptions (including medications for glaucoma) or over-the-counter (OTC) solutions (not including artificial tears), gels or scrubs for the duration of the trial (excluding medications allowed for the conduct of the trial);
- 11. Corrected visual acuity greater than or equal to logarithm of the minimum angle of resolution (logMAR) + 0.7 as assessed by Early Treatment of Diabetic Retinopathy Study (ETDRS) scale in both eyes at Visit 1;
- 12. Pregnancy, nursing, or planned pregnancy during the conduct of the trial;
- 13. Unwillingness to submit a urine pregnancy test at Visit 1 and Visit 3 (or early termination visit) if of childbearing potential. (Nonchildbearing potential is

Confidential Page 20 of 60

- defined as a woman who is permanently sterilized [e.g., has had a hysterectomy or tubal ligation], or is post-menopausal [without menses for 12 consecutive months]);
- 14. If of childbearing potential (female or male), unwillingness to use an acceptable means of birth control. (Acceptable methods of contraception include: hormonal oral, implantable, injectable, or transdermal contraceptives; mechanical spermicide in conjunction with a barrier such as a diaphragm or condom; intrauterine device [IUD]; or surgical sterilization of partner. For non-sexually active males or females, abstinence may be regarded as an adequate method of birth control; however, if the subject becomes sexually active during the study, he/she must agree to use adequate birth control as defined above for the remainder of the trial.);
- 15. Known allergy and/or sensitivity to the test article or its components;
- 16. A condition that the investigator feels may put the subject at significant risk, may confound the study results, or may interfere significantly with the subject's participation in the trial;
- 17. Current enrollment in an investigational drug or device study or have used an investigational drug or device within 30 days of Visit 1;
- 18. Use of reproxalap ophthalmic solution in the past year;
- 19. Current use of any medication known to cause ocular drying that is not used on a stable dosing regimen for at least 30 days prior to Visit 1;
- 20. Inability or unwillingness to follow instructions, including participation in all study assessments and visits.

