#### 4 OVERALL STUDY DESIGN

ADX-102-DED-023 is a Phase 3, multi-center, randomized, double-masked, parallel design, vehicle-controlled trial designed to evaluate the efficacy and safety of 0.25% Reproxalap Ophthalmic Solution compared to vehicle in subjects with dry eye disease. Approximately 350 subjects will be enrolled in the study. Male and female subjects at least 18 years of age with a subject-reported history of dry eye disease in both eyes and meeting all other eligibility criteria will be randomized to receive reproxalap or vehicle in a 1:1 ratio (approximately 150 subjects in each treatment group).

Visit 1 (Day -14 -16/+ 2): Screening	
 
Informed Consent
 
Demographics, Medical/Medication & Ocular History
 
Urine Pregnancy Testing (as needed)
 
Symptom Questionnaires, Ocular Dryness VAS, Visual Acuity
 
Slit Lamp Exam with Conjunctival Redness assessment
 
CAE exposure (90 minutes) with Ocular Dryness VAS, and Conjunctival Redness Assessment
 
Slit Lamp Exam with Conjunctival Redness assessment
 
Schirmer's Test
 
IOP and Dilated Fundoscopy
 

Visit 2 (Day 1): Randomization/Baseline	
 
Medical/Medication Update: AE Query
 
Visual Acuity
 
Slit Lamp Exam
 
Symptom Questionnaires at specified time points
 
Conjunctival Redness at specified time points
 
In-Office Doses (QID)
 
Tear Collection & Schirmer's Test at specified time points
 

Visit 3 (Day 2): CAE	
 
Medical/Medication Update: AE Query
 
Urine Pregnancy Testing (as needed)
 
Visual Acuity, Slit Lamp Exam
 
Symptom Questionnaires
 
Conjunctival Redness at specified time points
 

Confidential Page 18 of 60

CAE exposure (90 minutes) with Ocular Dryness
VAS, and and
Conjunctival Redness Assessments
Tear Collection at specified time points
IOP and Dilated Fundoscopy
Study Exit

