#### 8.1.2 Informed Consent

Prior to each subject's participation in the clinical trial (i.e., changes in a subject's medical treatment and/or study related procedures), the clinical trial will be discussed with the subjects, and subjects wishing to participate must give written informed consent using an informed consent form. The informed consent form must be the most recent version that has received approval/favorable review by a properly constituted Independent Review Board.

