#### 8.1.3 Washout Intervals

Prohibited medications, treatments, and activities are outlined in the exclusion criteria.

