#### 8.1.5 Methods for Assignment to Treatment Groups:

At Visit 1 each subject who signs the informed consent will be assigned a screening number. All screening numbers will be assigned in strict numerical sequence at each site and no numbers will be skipped or omitted.

At Visit 2, a patient who meets all the eligibility criteria will be randomized to receive reproxalap or vehicle in a 1:1 ratio. Patients will be assigned a randomization number and kit number via IWRS.

Both the randomization number and the assigned study drug kit number will be recorded on the patient's source document and eCRF.

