#### **8.3** Examination Procedures

# 8.3.1 Procedures to be Performed at the Study Visit with Regard to Study Objective(s)

#### Visit 1 (Day -14 -16/+2, Screening)

- Informed Consent and HIPAA
- Demographics (e.g., gender, date of birth, race, ethnicity)
- Medical/Medication & Ocular History
- Urine Pregnancy Test (as needed)
- Symptom Questionnaires:

Confidential Page 25 of 60

- Ocular Dryness Visual Analog Scale
- Visual Acuity (ETDRS)
- Slit Lamp Biomicroscopy with Conjunctival Redness assessment
- Fluorescein Staining
- Inclusion/Exclusion Criteria Review
- \_\_\_\_
- CAE Exposure (90 minutes, with:
- Slit Lamp Biomicroscopy with Conjunctival Redness assessment
- Schirmer's Test
- Intraocular Pressure
- Dilated Exam
- Schedule for Visit 2

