#### Visit 2 (Day 1, Baseline and In-Office Dosing)

- Medical/Medication Update
- Adverse Event Query
- Visual Acuity (ETDRS)
- Slit Lamp Biomicroscopy
- Symptom Questionnaires
- Conjunctival Redness Photography
- Inclusion/Exclusion Criteria Review
- Randomization/Enrollment
- Pre-Dose #1 Tear Collection (30 +/- 5 minutes pre-dose)
- In-Office Dose #1
- Post-Dose #1 Tear Collection (started within 10 + 2 minutes of dose) *Wait 3 hours between doses*

Confidential Page 26 of 60

- Pre-Dose #2 Tear Collection (30 +/- 5 minutes pre-dose)
- In-Office Dose # 2
- Post-Dose #2 Tear Collection (started within 10 + 2 minutes of dose) Wait 30 minutes between doses
- In-Office Dose #3
- Conjunctival Redness Photography (10 minutes +/- 2 minutes post-Dose #3)
- Symptom Questionnaires started within 10 minutes + 2 minutes post-

Wait 30 minutes between doses

- Pre-Dose #4 Schirmer's Test (10 +/- 2 minutes pre-dose)
  - Weigh Schirmer's Test strip before and after use
- In-Office Dose #4
- Post-Dose #4 Schirmer's Test (started within 5 +/- 2 minutes of dose)
  - Weigh Schirmer's Test strip before and after use
- Schedule for Visit 3

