# Visit 3 (Day 2, CAE■)

- Medical/Medication Update
- Adverse Event Query
- Urine Pregnancy Test (as needed)
- Visual Acuity (ETDRS)
- Slit Lamp Biomicroscopy
- Conjunctival Redness Photography
- Symptom Questionnaires:

- Pre-Dose #1 Tear Collection (30 +/- 5 minutes pre-dose)
- In-Office Dose #1 within 10 minutes prior to CAE Entry
- CAE Exposure (90 minutes) with:

Confidential Page 27 of 60

- In-Office Dose #2 (45 +/- 2 minutes into CAE exposure, administer by site staff)
- Post-CAE exit Tear Collection (started within 5 + 2 minutes)
- In-Office Dose #3 (started within 2 minutes post-tear collection)
- Symptom Questionnaires started within 10 minutes + 2 minutes post-Dose #3:

- Post-Dose #3 Tear Collection (started within 15 + 2 minutes of dose)
- Slit Lamp Biomicroscopy
- Intraocular Pressure
- Dilated Exam
- Study Exit

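### Exclusion criterion 10 admits users of IOP-lowering drops who agree to stop, and the visible schedules require no IOP reading between Visit 1 and the end of Visit 3

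*Combined protocol and SAP*

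**What the plan says.** Criterion 10 in Section 5.4, repeated in the synopsis, opens with "Use of and unwillingness to discontinue topical ophthalmic prescriptions (including medications for glaucoma" and goes on to cover over-the-counter products for the length of the trial. Use and unwillingness are joined, so both must be present for the subject to be excluded. None of the 20 exclusion criteria names glaucoma, ocular hypertension or an IOP limit.

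Section 8.1.3, on washout, gives no interval. It says only: "Prohibited medications, treatments, and activities are outlined in the exclusion criteria". Criterion 10 itself contains none.

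Section 8.1.2 requires consent before "changes in a subject's medical treatment and/or study related procedures". Section 8.1.5 places the signature at screening: "At Visit 1 each subject who signs the informed consent will be assigned a screening number".

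The Section 4 table lists "IOP and Dilated Fundoscopy" for Visits 1 and 3 only. Section 8.3.1 agrees. Visit 1 ("Day -14 -16/+2, Screening") ends with IOP and a dilated exam. Visit 2 lists visual acuity, a slit lamp exam, an adverse event query and an "Inclusion/Exclusion Criteria Review", but no IOP. Visit 3 lists "Intraocular Pressure" after the last dose, the last tear collection and the slit lamp exam.

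Section 10.4.1 takes as baseline the last available value before randomised treatment starts on Day 1. Section 10.4.9 summarises IOP by arm and visit, with changes or shifts where appropriate.

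**The concern.** Criterion 10 tells sites that a subject on glaucoma drops may enter by agreeing to stop. Other criteria behave differently: criterion 6 excludes recent cyclosporine or lifitegrast use within 90 days whatever the subject is willing to do, and criteria 4 and 7 set their own intervals. For glaucoma drops there is neither an interval nor a pressure check tied to the interruption.

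Two things are at stake. One is the safety of a subject whose pressure treatment is stopped for a trial that doses on only two days. The other is interpretation. If the Visit 1 reading was taken on treatment and the Visit 3 reading off it, a rise caused by stopping would enter the IOP change or shift summary as if it had arisen under the test article.

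**Working it through.** No power or alpha calculation applies. The check is a reading of the visit lists plus day arithmetic.

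1. **Who gets in.** Exclusion requires use and unwillingness together. A user who is willing to stop fails the second condition and is not excluded by criterion 10.

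2. **When the stop falls.** Consent is signed at Visit 1 and must precede treatment changes, so a stop made for the trial falls at or after Visit 1. The documents give no stop date.

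3. **Required IOP readings.** Visit 1: one. Visit 2: none. Visit 3: one, near the end. Doses given between the two readings: 4 on Day 1 + 3 on Day 2 = 7.

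4. **Gap between readings.** Visit 1 is nominally Day -14, with a window from -14 - 16 = Day -30 to -14 + 2 = Day -12. With no Day 0, the gap to Day 2 is:
   - earliest Visit 1: 30 + 2 - 1 = 31 days;
   - nominal: 14 + 2 - 1 = 15 days;
   - latest: 12 + 2 - 1 = 13 days.

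   If a Day 0 is counted, each figure is one day longer: 32, 16 and 14. The synopsis gives participation of 16-32 days, which matches the nominal and longest cases on that count. Because the stop can come at any time from Visit 1 onward, the gap is a ceiling on time off treatment without a required reading.

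5. **Baseline.** With no IOP listed at Visit 2, the Section 10.4.1 rule makes the Visit 1 value the IOP baseline on the visible schedule. It may be an on-drug value.

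6. **Effect on mean IOP (assumed inputs).** If a share p = 1-3% of subjects stop and IOP rises by w = 4-8 mmHg, the mean change moves by p × w: from 0.01 × 4 = 0.04 to 0.03 × 8 = 0.24 mmHg. Randomisation gives both arms the same expected share of stoppers, so the expected difference between arms is unaffected.

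7. **Whether outliers can be counted.** Take p and w as above, 350 subjects (3.5 to 10.5 stoppers), and an assumed cut-off of a 10 mmHg rise. The result then turns on the assumed SD of IOP change, using P(rise ≥ 10) = 1 - Φ((10 - w)/SD):
   - SD 3: stoppers 3.5 × 0.0228 = 0.08 to 10.5 × 0.2525 = 2.65; background with no stopping, 350 × 0.00043 = 0.15.
   - SD 4: stoppers 3.5 × 0.0668 = 0.2 to 10.5 × 0.3085 = 3.2; background 350 × 0.0062 = 2.2.

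   A change of 1 mmHg in an assumed SD raises the background about fourteenfold, and the documents give none of these inputs.

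8. **Screening cost of excluding these users.** Section 5.1 plans about 600 screened for about 350 enrolled. Extra screening = 600/(1 - p) - 600, which is 6.1 at p = 0.01 and 18.6 at p = 0.03. The share p is again an assumption.

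**The case against.** The strongest reply is that the investigator already has what is needed. Visit 1 collects ocular and medication history, IOP and a dilated exam, and criterion 16 allows exclusion of anyone judged at significant risk. Eligibility is reviewed again at Visit 2 before randomisation. Section 5.5 allows withdrawal for safety, Section 8.4.2 allows IOP at an unscheduled visit, and a subject discontinued before Visit 3 should have the Visit 3 safety evaluations, which include IOP. The sponsor named glaucoma drugs in the criterion, so willingness to stop looks like a deliberate choice.

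Most of this stands as mitigation. It does not close the gap: criterion 16 and unscheduled IOP are discretionary, the Visit 2 examinations do not measure pressure, and the early-termination provision covers only subjects who leave and itself allows investigator discretion.

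A second reply is that withheld text may answer the point. Appendix 1 and the IOP procedure are blank in this copy, and the visible inclusion list stops at item 4. An IOP check or limit could sit there. This stands as a limit on the finding, although the legible lists in Sections 4 and 8.3.1 agree with each other.

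A third is that an IOP reading at Visit 2 would answer the missing measurement more directly. It would, but it would leave the interruption of treatment in place.

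A reader might also infer that these subjects are untreated for 13 to 31 days. The documents do not support that. Someone who stops shortly before Visit 2 is off treatment for only a few days by Day 2.

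**Conclusion.** The point holds as a minor matter of subject safety and interpretation. As written, criterion 10 permits IOP-lowering treatment to be stopped for the trial, with no washout interval and, on the visible schedules, no required IOP reading until the end of Visit 3. The longest such period is 31 days, or 32 if a Day 0 is counted.

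Two stronger readings should be set aside. A reader might infer a predictable number of IOP outliers. The documents give no share of users, size of rise, SD or cut-off, and plausible assumed values put the trial-level figure anywhere from below background to above it. A reader might also infer that the trial's conclusions are at risk. Nothing supports that: stopping before the first dose is balanced in expectation by randomisation, the efficacy endpoints do not use IOP, and the shift in mean IOP is at most 0.24 mmHg even under the larger assumed values.

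The conclusion depends on Appendix 1 and any withheld inclusion items adding no IOP check or limit.

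**What to change.** Reword criterion 10, in Section 5.4 and in the synopsis, so that a subject using IOP-lowering ophthalmic medication at Visit 1 is excluded regardless of willingness to stop. Leave the rest of the criterion unchanged, so willingness to stop still governs other topical prescriptions and over-the-counter products.

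The cost is one clause in the next amendment and a few more screen failures: about 6 to 19 more people screened on 600, if 1-3% are affected. That is a cheap improvement for a trial that doses on two days.

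For subjects already enrolled, list those who stopped IOP-lowering drops alongside their IOP change. Do this only where the medication updates recorded a stop date. Section 8.2 requires the use of concurrent medication and its reason to be recorded but does not expressly require stop dates, so the list may be incomplete and should say so.

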# **SYNOPSIS**

Protocol Title:	The TRANQUILITY 2 Trial: A Multi-Center Randomized, Double-Masked, Parallel Design, Vehicle-Controlled Phase 3 Clinical Trial to Assess the Efficacy and Safety of 0.25% -Reproxalap Ophthalmic Solution Compared to Vehicle in Subjects with Dry Eye Disease	
Protocol Number:	ADX-102-DED-023	
Investigational Product:	0.25% Reproxalap Ophthalmic Solution (reproxalap)	
Study Phase:	3	
Primary Objective(s):	To evaluate the efficacy of reproxalap, as assessed by conjunctival redness, Schirmer's Test, and symptoms after dosing prior to and during exposure to the with dry eye disease	
Overall Study Design:		
Structure:	Multi-center, double-masked, randomized parallel design trial	
Duration:	An individual subject's participation is estimated to be approximately 16-32 days.	
Controls: Vehicle Ophthalmic Solution (vehicle)		
Dosage/Dose Regimen:	Test article (reproxalap or vehicle) will be dosed topically in both eyes.  Test article will be administered QID on Day 1 (Visit 2). On Day 2 (Visit 3), test article will be administered once within 10 minutes prior to the CAE entry, once 45 minutes after initiation of the CAE, and once at CAE exit.	
Summary of Visit Schedule:	Three visits over the course of approximately 2 weeks:  • Visit 1 = Day -14 -16/+2, Screening	

Confidential Page 3 of 60

 
Visit 2 = Day 1, Randomization/Baseline
 
Visit 3 = Day 2 CAE & Study Exit
 
Subjects will be randomized 1:1 to receive reproxalap or vehicle.
 
Measures Taken to Reduce Bias:
 
ADX-102-DED-023 is a randomized treatment assignment, double-masked trial.
 
			
Study Population Characteristics:			
Number of Subjects:	Approximately 350 subjects are expected to be enrolled in the trial.		
Condition/Disease:	Dry Eye Disease (DED)		
Inclusion Criteria:	
 
Subjects must meet all of the following criteria:
 
1. 18 years of age (either gender and any race);
 
2. Ability to provide written informed consent and sign the Health Information Portability and Accountability Act (HIPAA) form;
 
3. Reported history of dry eye for at least 6 months prior to Visit 1;
 
4. Reported history of use or desire to use eye drops for dry eye symptoms within 6 months of Visit 1;
 
		
Exclusion Criteria:	Subjects must not meet any of the following criteria:		

Confidential Page 4 of 60

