#### 6 STUDY PARAMETERS

#### 6.1 Primary Endpoint

- Schirmer's Test overall mean change from baseline (CFB) before and after the fourth dose on Day 1
- Schirmer's Test greater than or equal to 10mm responder analysis of change from baseline before and after the fourth dose on Day 1

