# **6.3** Secondary Endpoints

- Overall mean CFB of Conjunctival Redness over 90 minutes in the CAE at Day 2
- Overall mean CFB of Eye Dryness (VAS; Visual Analog Scale) over 90 minutes in the CAE at Day 2
- Overall mean CFB of Eye Dryness (VAS) assessed over Days 1 and 2 (excluding CAE)

Confidential Page 22 of 60

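### No pregnancy test is scheduled at randomisation: the last one is 12 to 30 days old, and the next comes after four of seven doses

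*Combined protocol and SAP*

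**What the plan says.** Exclusion 12 (Synopsis and Section 5.4) bars "Pregnancy, nursing, or planned pregnancy during the conduct of the trial". Section 8.1.5 ties eligibility to the randomisation visit: "At Visit 2, a patient who meets all the eligibility criteria will be randomized to receive reproxalap or vehicle in a 1:1 ratio".

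Exclusion 13, in both places, names the visits at which a test is expected: "Unwillingness to submit a urine pregnancy test at Visit 1 and Visit 3 (or early termination visit) if of childbearing potential". The Section 4 table lists "Urine Pregnancy Testing (as needed") under Visit 1 and Visit 3 only. The Section 8.3.1 procedure lists show the same pattern. Visit 2 has a review of the inclusion and exclusion criteria before randomisation, but no pregnancy test.

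On dosing, the Synopsis states "Test article will be administered QID on Day 1 (Visit 2"), followed by three doses on Day 2. In the Visit 3 list the urine test comes before the first Day 2 dose.

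Two other provisions matter. Exclusion 14 covers contraception: "If of childbearing potential (female or male), unwillingness to use an acceptable means of birth control". The Early Termination/Discontinuation text in Section 8.3.1 requires a subject found to be pregnant to be withdrawn, and requires the investigator to request the related medical reports and document the outcome of the pregnancy.

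**The concern.** The schedule does not contradict itself; the sources that can be read agree. The question is where the second test sits.

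When a woman of childbearing potential is randomised, exclusion 12 rests on three things: a screening test done some weeks earlier, what she knows and reports at the Visit 2 review, and the contraception requirement. Together these remove pregnancies that were detectable at Visit 1 or known by Visit 2, and they make conception in between less likely. They do not catch a pregnancy too early to detect at Visit 1, or a contraceptive failure of which she is unaware. Such a subject would receive all four Day 1 doses before being tested again.

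The protocol already provides for a second test. Placed on Day 2, that test mostly reports her status on Day 1, when the result could still have prevented exposure.

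There is also a small data consequence. A positive test before randomisation is a screen failure. A positive test at Visit 3 is a discontinuation after randomisation: under Section 10.1 she stays in the ITT population, but without data in the CAE (the 90-minute Day 2 exposure).

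**Working it through.** **Inputs**

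| Input | Value | Source |
|---|---|---|
| Visit 1 window | Day -14, -16/+2 | Synopsis; Sections 4 and 8.3.1 |
| Randomisation and first dose | Day 1 (Visit 2) | Sections 8.1.5 and 8.3.1 |
| Scheduled pregnancy tests | Visits 1 and 3 | Exclusion 13; Sections 4 and 8.3.1 |
| Doses | 4 on Day 1, 3 on Day 2 | Synopsis; Section 8.3.1 |
| Stated participation | about 16 to 32 days | Synopsis |
| Planned enrolment | about 350 | Synopsis; Section 5.1 |

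**1. Day-numbering convention.** The window runs from -14 - 16 = Day -30 to -14 + 2 = Day -12. With no Day 0, the inclusive span from Day -d to Day 2 is d + 2 days.

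- From Day -14: 14 + 2 = 16.
- From Day -30: 30 + 2 = 32.

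This reproduces the stated 16 to 32 days, with the lower end taken from the nominal screening day. With a Day 0 the spans would be 17 and 33, which do not match. The calendar without a Day 0 is therefore the better reading.

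**2. Age of the last test at first dose.** With no Day 0, the time elapsed from Day -d to Day 1 is d days.

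- Earliest screening: 30 days.
- Nominal: 14 days.
- Latest screening: 12 days.

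Counting a Day 0 would add one day to each (31, 15 and 13).

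**3. Doses given before the next test.** Total doses are 4 + 3 = 7. The Visit 3 test is listed before the first Day 2 dose, so 4/7 = 57% of doses precede it. With a test at the Visit 2 review, before randomisation, the figure is 0/7.

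**4. Number of tests per woman of childbearing potential.** Two now; two if the Visit 3 test is moved to Visit 2; three if a Visit 2 test is added and the exit test is kept.

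**5. Subjects affected (assumption only).** The protocol gives neither the number of women of childbearing potential nor a rate of undetected pregnancy. Suppose 10% to 40% of 350 (35 to 140 subjects) are of childbearing potential, and 0.1% to 1% of them have an undetected pregnancy at Visit 2.

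- Low: 35 × 0.001 = 0.035, about 0.04 subjects.
- High: 140 × 0.01 = 1.4 subjects.
- With 1:1 allocation, those receiving reproxalap: about 0.02 to 0.7 subjects.

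**6. Endpoints affected.** Both primary endpoints are Schirmer measures taken "before and after the fourth dose on Day 1", so they are complete before the Visit 3 test. Third in the testing sequence is "Overall mean CFB of Conjunctival Redness over 90 minutes in the CAE at Day 2"; fourth is eye dryness in the same exposure. Both would be missing for a subject withdrawn at the start of Visit 3. The fifth, eye dryness over Days 1 and 2 outside the CAE, would lose its Day 2 part. At the assumed maximum this is 1.4/350 = 0.4% of subjects.

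**The case against.** The strongest reply is that this is a preference about timing and not an error. Nothing in the protocol requires a test on the day of dosing. Several safeguards exist: the screening test, the contraception criterion, the exclusion of planned pregnancy, the Visit 2 medical update and criteria review, a test listed before Day 2 dosing, and withdrawal with outcome follow-up. Section 8.4.2 also allows a urine test at an unscheduled visit. Few subjects are at issue, half would receive vehicle, exposure is to four topical doses of a 0.25% solution, and the legible text contains no reproductive-toxicity or systemic-exposure information. Moving the test would also remove the only one scheduled after dosing starts.

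Much of this stands. The expected count is small and rests on assumed inputs, the documents do not establish how harmful the exposure would be, and the effect on the data is negligible. It is also correct that moving the test is free of added procedures only if the exit test is given up.

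It does not answer the point about placement. Contraception and self-report are not verification, an unscheduled-visit test is optional, and the Visit 3 test can spare the three Day 2 doses but not the four on Day 1. A test done one day later can be expected to find very little that a Day 1 test would miss, so little is lost by moving it. The protocol itself treats pregnancy as a reason not to be dosed, so the case for testing first does not depend on toxicity data.

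**Conclusion.** The concern holds. At randomisation the pregnancy exclusion is supported by a test 12 to 30 days old (nominally 14), and four of the seven doses precede the next one. The schedule is internally consistent. The weakness is that the second test can detect Day 1 exposure but cannot prevent it.

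Confidence in the schedule facts is high. Appendix 1 cannot be read in the public text, but exclusion 13, the Section 4 table and the visit lists all agree. The number of subjects, 0.04 to 1.4 of 350, rests entirely on assumed proportions and shows only that few would be affected. Sample size and alpha do not change. The sponsor should make the change because it removes an avoidable exposure at almost no cost, not because it threatens the trial's conclusions.

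**What to change.** Move the second urine test from Visit 3 to the Visit 2 eligibility review, before randomisation and Dose #1. Specifically:

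- Reword exclusion 13, in the Synopsis and in Section 5.4, to name Visit 1 and Visit 2.
- Change the Section 4 table and the Section 8.3.1 lists for Visits 2 and 3 to match, and check Appendix 1 against them.
- State explicitly whether the early-termination test stays. Exclusion 13 currently pairs it with Visit 3, and early termination repeats the Visit 3 safety evaluations.

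The cost is protocol wording and schedule only, with no added procedure and the loss of an exit test that would fall one day later. If the sponsor prefers to retain the exit test, the cost is one further urine test per woman of childbearing potential (three instead of two).
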